10.9 Other statistical considerations

In addition to the main analyses described above, we also plan to undertake extensive statistical analysis to explore whether combining VOC data with faecal calprotectin and possibly other inflammatory markers (e.g. CRP) increases sensitivity and specificity in the diagnosis of IBD. Multivariate logistic regression models will be used to determine the specificities and 95% confidence intervals of combinations of diagnostic tests and also explore the effects of demographic factors such as age, sex and region. Other statistical methods will be used if deemed necessary.

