STUDY FLOW CHART

VOCs in pIBD Flow chart

Study timeline

A. Study preparation: April - September 2017 (6 months)

- Study preparation will start on April 1st
- Ethical approval secured by end of July 2017
- SOPs and CRFs completed by end of August 2017
- Study database completed by end of September 2017
- Site-set-up and training completed by end of September 2017

B. Recruitment and follow-up: October 2017 - end of March 2018

- Recruitment across 3 sites (3-4 IBD cases and 3-4 non-IBD controls/centre/month).
- Follow-up of last cases for 3 months (Jan 2019 March 2019)

C. Analyses

- Measurement of faecal VOCs completed by end of March 2019
- Statistical analysis to determine VOCs profiles completed by end of April 2019
- Statistical analysis combining VOCs profile with demographic, clinical and environmental data completed by end of June 2019

D. Writing-up and presentation of findings

• Final report submitted by end of September 2019

STUDY PROTOCOL

Evaluation of faecal volatile organic compounds in the diagnosis of paediatric inflammatory bowel disease

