The data (chromatograms and fragmentation patterns) will be analysed using AMDIS software and the current NIST library of over 240,000 compounds. Project–specific libraries of compounds will be used to generate reports for each group of children – those with CD, UC and other pathologies. Metab software (Aggio 2011) will be used to align the reports. Metaboanalysis software (Xia 2009) will be used to compare the abundance of each VOC in each group: the software will report the false discovery rate (FDR) allowing comparison of datasets of this kind. ANOVA will be performed in the same way. We will produce summaries of the data describing the fold changes, FDR, sensitivity, specificity and ROC curves for compounds and models derived from them. This method uses equipment that is available in hospital clinical chemistry laboratories.

For the second method, the stool sample will be analysed by our GC-sensor (Odoreader©). This is more rapid than the first method and generates a VOCs profile (rather than identifying individual VOCs). 450mg of faeces are heated within the device, and the emitted gases passed through a GC column. On leaving the column, the VOCs pass perpendicular to a metal oxide sensor unit. A current is passed across the sensor and its resistance is determined by the presence of VOCs. Consequently the sensor output (current) is a representation of the VOCs in the sample (with an output similar to a chromatogram). We have a well-defined algorithm that removes the baseline, normalises the data and performs retention time correction before comparing the profiles derived from two groups of samples using wavelets. The data is then reported as sensitivity, specificity and AUROC of a model using state of the art modelling tools including support vector machine polynomial (SVMpoly) with double cross validation and Monte Carlo randomisation (Aggio 2016).

Stool samples will be stored frozen for up to 5 years for possible use in ancillary studies. Stool samples collected from participants as part of this study will be transported, stored, accessed and processed in accordance with national legislation relating to the use and storage of human tissue for research purposes and such activities shall at least meet the requirements as set out in the 2004 Human Tissue Act and the 2006 Human Tissue (Scotland) Act.

In the version of the protocol, we will also investigate the fungal mycobiome.

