10.3.2 Primary outcome analysis

For the VOCS identified by GCMS, consistent with our findings in adults (Ahmed 2016), we anticipate identifying a small number of VOCs that can be used to diagnose IBD and distinguish IBD from other common pathologies including functional abdominal conditions.

For the results generated by the GC-sensor (Odoreader©), we will compare the faecal VOC profile in children in whom IBD is confirmed with that in children with alternative diagnoses according to the advanced statistical methods required for determining and comparing VOC profiles (Aggio 2016).

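### Section 10.9 estimates the gain from adding VOCs to calprotectin by ordinary logistic regression in the same children whose diagnoses shaped the VOC model, and names no validation of the combination

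*Protocol*

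**What the plan says.** Protocol section 10.9 sets an additional analysis to "explore whether combining VOC data with faecal calprotectin and possibly other inflammatory markers (e.g. CRP) increases sensitivity and specificity". It names the estimator: "Multivariate logistic regression models will be used to determine the specificities and 95% confidence intervals of combinations of diagnostic tests". It does not say what form the VOC input takes, and it names no resampling or held-out step for the combined model.

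The study timeline puts two analyses in sequence: "Statistical analysis to determine VOCs profiles completed by end of April 2019", then "Statistical analysis combining VOCs profile with demographic, clinical and environmental data completed by end of June 2019".

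The VOC side is learned from diagnosis in this study:

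- **GC-sensor (7.11).** The algorithm works by "comparing the profiles derived from two groups of samples using wavelets". Its performance is reported from a model using "support vector machine polynomial (SVMpoly) with double cross validation and Monte Carlo randomisation".
- **GC-MS (7.11, 10.3.2).** Section 7.11 promises "sensitivity, specificity and ROC curves for compounds and models derived from them" and names no cross-validation for this method. Section 10.3.2 adds: "we anticipate identifying a small number of VOCs that can be used to diagnose IBD".

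Section 10.7 puts every participant with a completed VOC analysis into the analysis, and no training and validation split is stated.

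**The concern.** Calprotectin and CRP are existing markers. In the logistic model each needs only a coefficient. A VOC score or panel has already been fitted to, or chosen by, the outcome that the logistic model then predicts. Entered as it stands, it carries that fit into the second model, so the optimism runs in one direction: towards VOCs and away from calprotectin.

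Cross-validating the stand-alone VOC model gives an honest figure for that model. It does not protect a second model that takes the fitted score as a covariate. Ordinary logistic intervals also treat the score as fixed in advance, so they leave out the uncertainty from selection and training.

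Section 1 of the protocol gives the low specificity of calprotectin as the reason for seeking an alternative or additional test. Section 10.9 is where the additional role is examined, so a gain produced by re-use of the data would bear directly on that question.

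**Working it through.** **1. The plan's own figure.** Section 10.1 sizes the study on specificity 0.80 for VOCs against 0.68 for calprotectin. A one-sample comparison with a fixed 0.68, two-sided 5%, 80% power and variance at 0.80 gives (1.960 + 0.842)² × 0.80 × 0.20 / 0.12² = 87.2, so 88, as stated. This point does not affect that number. The 0.12 difference is a useful yardstick for what follows.

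**2. Inputs.** From the documents: 143 IBD cases and a similar number of controls (10.2; total 286 in 10.1), and calprotectin sensitivity 0.98 and specificity 0.68 (10.1).

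Assumed:

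- 20 to 200 independent VOC features, all pure noise.
- A score from the five most different compounds, from a linear ridge profile, or from a quadratic-kernel classifier standing in for the planned support vector machine.
- 10 folds for the out-of-fold scores.
- Specificity read at 98% sensitivity, a cut-off that 10.9 does not set.

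**3. Model.** Calprotectin is normal with unit SD in both groups, separated by 2.054 + 0.468 = 2.522 SD, the sum of the normal quantiles for 0.98 and 0.68. A logistic model of diagnosis on calprotectin plus the standardised VOC score is compared with calprotectin alone in the same simulated study. Since 0.98 × 143 = 140.1, 141 cases must lie at or above the cut-off (141/143 = 0.986), which is why calprotectin alone averages slightly under 0.68.

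**4. Results: mean specificity with VOCs that carry no information.**

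| VOC score (features) | Calprotectin alone | + in-sample score | Gain | + out-of-fold score | Gain | VOC term p<0.05: in-sample / out-of-fold |
|---|---|---|---|---|---|---|
| Top 5 (20) | 0.664 | 0.680 | 0.016 | 0.664 | 0.000 | 51% / 13% |
| Top 5 (50) | 0.655 | 0.685 | 0.030 | 0.665 | 0.010 | 73% / 11% |
| Top 5 (100) | 0.665 | 0.692 | 0.027 | 0.668 | 0.003 | 85% / 13% |
| Top 5 (200) | 0.662 | 0.690 | 0.028 | 0.669 | 0.007 | 89% / 18% |
| Ridge (20) | 0.664 | 0.693 | 0.029 | 0.667 | 0.003 | 71% / 8% |
| Ridge (100) | 0.658 | 0.786 | 0.128 | 0.666 | 0.008 | 100% / 15% |
| Ridge (200) | 0.643 | 0.925 | 0.282 | 0.646 | 0.003 | 100% / 14% |
| Kernel (20) | 0.645 | 0.911 | 0.266 | 0.651 | 0.006 | 100% / 1% |
| Kernel (100) | 0.664 | 1.000 | 0.336 | 0.667 | 0.003 | 100% / 8% |
| Kernel (200) | 0.661 | 1.000 | 0.339 | 0.670 | 0.009 | 100% / 9% |

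There were 150 replicates for top 5 and 100 for the others, so a percentage near 50% with 150 replicates has a standard error of about √(0.25/150) = 4 points.

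**5. Three readings of the table.**

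- Applied to new children at 98% sensitivity, the in-sample rules reach only 0.65 to 0.67 (top 5), 0.22 to 0.65 (ridge) and 0.07 to 0.21 (kernel). The gain is not real, and a flexible rule does worse than calprotectin alone.
- One VOC fixed in advance and entered raw shows no gain (0.660 against 0.662; significant in 6% of 200 replicates). The problem comes from learning on the same outcomes, not from logistic regression itself.
- Out-of-fold scores remove the mean specificity gain, but the ordinary p-value for the VOC term is still not a 5% test (1 to 18%). It should not be used as the evidence of added value.

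**6. Limits of the check.** The five compounds entered the model as one fitted score. Entering them as five covariates was not simulated. That the intervals are too narrow follows from their treating the score as fixed; coverage was not simulated.

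**The case against.** The strongest reply is that 10.9 speaks only of VOC data. That could mean individual compounds, raw sensor output or held-out predictions. The timeline's VOC profile is also ambiguous, because elsewhere the protocol uses the term for what the sensor produces. The double cross-validation in 7.11 could supply a held-out prediction for every child, and with such predictions the simulated gain is at most 0.01. The analysis is exploratory, 10.9 allows other methods, and section 10 promises a separate SAP that may fix the input.

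Much of this stands. A reader might infer that the plan commits to an in-sample score, so that VOCs are bound to show a gain even if uninformative. The documents do not support that. No section says that a resubstituted score is carried forward, and even an in-sample five-compound score raised specificity in only 58 to 65% of replicates. The rise to 1.00 belongs to a flexible stand-in model on assumed features, while 10.3.2 expects a small number of compounds from GC-MS.

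Two things remain. The protocol has not simply left the matter open: it has already chosen ordinary logistic regression as the source of the specificities and their intervals, after a step that derives the VOC profile. And 7.11 attaches its cross-validation to the reported performance of the GC-sensor model; it does not say that held-out scores pass to 10.9, and it names no cross-validation for GC-MS models. Section 5 places the VOC statistics and the clinical-data analysis in different institutions. This suggests, though it does not show, that a finished VOC result will be handed over unless the plan says otherwise.

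**Conclusion.** The concern holds conditionally. As written, 10.9 permits a VOC score or panel learned from these children's diagnoses to be combined with calprotectin in the same children without validation. If that is done, the added value of VOCs is biased upward and the intervals are too narrow. With uninformative VOCs, the spurious gain in specificity at 98% sensitivity is about 0.02 to 0.03 for a small selected panel, with frequent false significance. For a flexible resubstituted profile it reaches about 0.3, well beyond the 0.12 on which the study was sized. With out-of-fold scores there is practically no gain.

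These sizes rest on the assumed feature counts, independent noise features, the stand-in classifiers and the 98% sensitivity cut-off. They show what could happen under the present wording and do not predict the study's result. The primary comparison and the figure of 88 are not touched. The change is worth making because it is cheap and the combined result speaks to the use of VOCs as an additional test.

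**What to change.** In 10.9, for both GC-MS and the GC-sensor:

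- **VOC input.** State that it is each child's out-of-fold prediction, from a VOC model selected and fitted without that child.
- **Evaluation.** Assess VOC selection or training, the logistic combination and the cut-off together in the same outer cross-validation folds. Within each outer training set, inner folds supply the VOC scores used to set the coefficients and the cut-off. The held-out children are then scored once. This extends the scheme already named in 7.11.
- **Intervals.** Obtain the 95% CI by resampling children and repeating the whole pipeline, with all copies of a child kept in the same fold. This condition matters. In a separate noise simulation (quadratic kernel; 50, 150 and 300 features; 60 replicates), bootstrap samples with folds assigned by row gave mean combined specificity 0.80, 0.81 and 0.84, against 0.68, 0.67 and 0.65 for calprotectin alone. With folds kept by child it was 0.68, 0.68 and 0.66.

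The cost is a few lines of text, extra computing, and a scheme shared between the teams handling VOC and clinical data. The reported gain from combining tests is likely to be less favourable, and the analysis remains exploratory.

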10.11 Economic evaluation: N/a

11 DATA HANDLING

11.1 Data collection tools and source document identification

Clinical and laboratory information required for the study will be extracted from patient medical records. Information about environmental factors will be collected by questionnaire. All study data will be recorded onto standardized paper case report forms. Participants will be followed-up by telephone call if any data is incomplete.

Case report forms for all participating patients and signed informed consent forms will be stored securely at the hospital sites.

11.2 Data handling and record keeping

Participants in the study will be allocated a unique, site-specific study number. Personal identifiers will be recorded only on the participant log and linked to the case report forms by the participant's initials and study number.

Baseline and outcome information will be collected by the research nurse and checked with the child's clinician or specialist nurse.

Data collection will use paper forms. Data from the CRFs will be entered at each site by the research nurse into an electronic database. Data transfer from the hospital sites to LSTM will be by established and secure LSTM procedures. The Data Manager will monitor data quality and ensure adequate data back-up. Data analysis will be undertaken by the study statistician.

No data will be transferred outside of the EEA.

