5 STUDY SETTING

Recruitment of children will be undertaken in 3 paediatric gastroenterology referral centres in the UK: Alder Hey Children's Hospital, Liverpool; Bristol Royal Hospital for Children, Bristol; and Birmingham Children's Hospital, Birmingham.

Laboratory analyses and statistical analysis to determine and compare faecal VOCs between groups will be done in the Institute of Translation Medicine, University of Liverpool. Management and analysis of clinical data will take place at the Liverpool School of Tropical Medicine.

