7.3 The randomisation scheme: N/a

7.3.1 Method of implementing the allocation sequence: N/a

7.4 Blinding

Laboratory staff performing the faecal VOCs analysis will be blinded to the patient's diagnosis and response to treatment in those with IBD.

Faecal VOCs results will not be available to clinical staff who are making diagnoses and assessing response to treatment in IBD.

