13.7 Data protection and patient confidentiality

All investigators and study site staff will comply with the requirements of the Data Protection Act 1998 with regards to the collection, storage, processing and disclosure of personal information and will uphold the Act's core principles.

Faecal volatiles in children with inflammatory bowel disease

Personal information will be collected by members of the research team. Participants in the study will be allocated a unique, site-specific study number. Personal identifiers will be recorded only on the participant log and linked to the case report forms by the participant's initials and study number.

Paper forms will be kept in locked cabinets in offices with restricted access. Digital data will be kept on password protected computers and storage media and transmitted through secure means between sites. Data will be stored for a minimum of 5 years after the publication of results. The Sponsors are the custodians of the data.

13.8 Financial and other competing interests for the chief investigator, PIs at each site and committee members for the overall trial management

The chief investigator, PIs at each site and committee members for the overall study management do not have any financial and other competing interests.

The University of Liverpool and University of West of England jointly own IP around the GC-sensor. This is protected by a US patent. IP is owed by University of Liverpool regarding the GC-Sensor analytical pathway / software. The Business Gateway at University of Liverpool will be responsible for agreeing terms with NIHR to ensure new IP generated by this work will be recognised and exploited in link with the terms and conditions of the funding. University of Liverpool spun out a company, Nidor Diagnostics, to commercialise the technology. The Board includes two non-executives with experience of commercialising diagnostic IP. They will be responsible for working through the regulatory steps in UK, Europe and US.

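### The primary VOC comparison sits with the university that is commercialising the GC-sensor, and nothing requires processing to be locked before diagnoses are known

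*Protocol*

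**What the plan says.** - **Who compares the groups.** Protocol section 5 states that "statistical analysis to determine and compare faecal VOCs between groups will be done in the Institute of Translation Medicine, University of Liverpool". The laboratory analyses are placed there too. The next sentence of section 5 reads "Management and analysis of clinical data will take place at the Liverpool School of Tropical Medicine".
- **Who analyses the data.** Section 11.2, at the end of a paragraph on CRF entry and transfer to LSTM, states "Data analysis will be undertaken by the study statistician". The contacts table places the statistician at LSTM.
- **Who is blinded.** Section 7.4 states "Laboratory staff performing the faecal VOCs analysis will be blinded to the patient's diagnosis", and extends this to treatment response in IBD. It also keeps VOC results from the clinicians who make the diagnoses. It does not mention whoever carries out the group comparison.
- **How the data are processed.** In 7.11, GCMS reports are generated separately for CD, UC and other pathologies, and the reports are then aligned. For the GC-sensor, a defined algorithm removes baseline, normalises and corrects retention time, after which two groups of profiles are compared. Modelling uses tools that include a polynomial support vector machine, with double cross validation and Monte Carlo randomisation.
- **Who has an interest.** Section 13.8 says the chief investigator, site PIs and management committee members "do not have any financial and other competing interests". It then says "The University of Liverpool and University of West of England jointly own IP around the GC-sensor", that the University of Liverpool owns the analytical software IP, and that "University of Liverpool spun out a company" to commercialise the technology.

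**The concern.** IBD versus non-IBD VOCs at presentation is the primary outcome. The institution that runs the stools also compares the groups, and it has a commercial stake in one of the two measurement methods. To compare groups it must hold the diagnoses. If it holds them while the data are still being processed, then run exclusions, re-runs, peak handling, normalisation and choice of model can all be influenced by how well the result separates the groups.

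Double cross validation does not close this gap. It guards against overfitting inside one fixed pipeline, not against choosing between pipelines after their accuracy has been seen. The result at stake is the study's headline sensitivity and specificity. A reader of the published result would want to know that the test's owner could not tune it against known diagnoses.

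**Working it through.** The protocol gives no figure on this point, so the check is mainly a comparison of sections.

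**1. Is the primary comparison placed with the owner?** Yes. Section 5 puts the VOC group comparison at the University of Liverpool, sections 3.3 and 10.3.2 make that comparison the primary outcome, and section 13.8 names the same university as co-owner and commercialiser of the GC-sensor.

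**2. Does the 7.4 blind cover the comparison?** Not on its wording. It names laboratory staff performing the VOC analysis. The protocol does not say whether those who compare the groups are different people.

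**3. Does processing need the diagnosis?** For GCMS, as written, yes: 7.11 generates reports by diagnostic group first and aligns them afterwards. The label therefore enters before the data set is final. This sits badly with 7.4. For the GC-sensor, the pre-processing is described as coming before the two-group comparison, so the label need not enter until then. No step fixes the processed data before that comparison.

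**4. Are the diagnoses available in time?** Yes. Under 7.11, VOC analysis is performed at the end of the study. Under 7.7, diagnoses are recorded at 3 months after recruitment. Most diagnoses will exist when the samples are run. The timeline ends both follow-up and VOC measurement in March 2019 and the VOC-profile statistics in April 2019, with no lock between them.

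**5. Who runs the comparison under 11.2?** Two readings are possible. If 11.2 covers all data, it does not fit section 5. If it covers the CRF data sent to LSTM, it agrees with section 5, and with the timeline, which lists VOC-profile analysis and the combined analysis as separate steps. On the second reading the primary comparison rests wholly with the owning university.

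**6. Illustration of size (assumptions, not protocol figures).** Suppose *k* processing variants give specificity estimates with common correlation ρ, and the best is kept.
- Non-IBD children: 286 − 143 = 143 (sections 10.1 and 10.2). True specificity is taken as 0.68, the calprotectin value in 10.1.
- SE = √(0.68 × 0.32 / 143) = 0.0390.
- Mean inflation = E[max of *k* independent standard normals] × √(1 − ρ) × SE. The expected maximum is 1.163 for *k* = 5 and 1.539 for *k* = 10.
- Example: *k* = 5, ρ = 0.5 gives 1.163 × 0.707 × 0.0390 = 0.032.
- The chance of wrongly declaring better than 0.68 is P(max > 1.96), against 2.5% one-sided for a single pre-set pipeline.

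| k | ρ | Inflation (points) | Chance of false claim |
|---|---|---|---|
| 5 | 0.5 | 3.2 | 9.1% |
| 5 | 0.8 | 2.0 | 6.4% |
| 5 | 0.9 | 1.4 | 5.1% |
| 10 | 0.5 | 4.2 | 14.4% |
| 10 | 0.8 | 2.7 | 8.6% |
| 10 | 0.9 | 1.9 | 6.4% |

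For scale, the gain the study is sized to show is 0.80 − 0.68 = 12 points.

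**The case against.** **Sections 5 and 11.2 do not conflict.** In context, 11.2 closes a paragraph on CRF data going to LSTM, and section 5 divides VOC work from clinical work. This stands: a reader might infer a flat contradiction, but the text supports only an ambiguity.

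**Section 13.8 hides nothing.** A reader might infer that its nil declaration is contradicted by the paragraph that follows. The documents do not show that. The declaration concerns individuals, the institutional interest is openly disclosed beside it, and no section says that any TMG member holds shares, royalties or a board seat. The Laboratory Supervisor sits on the TMG, but that person's employer can only be inferred from where the laboratory is. Clarification is warranted; a charge of false declaration is not.

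**The interest is narrower than the primary outcome.** This also stands. The disclosed IP concerns the GC-sensor and its software; 7.11 describes GCMS as using equipment available in hospital laboratories. The missing lock applies to both methods, the commercial interest only to one.

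**Safeguards exist.** The 7.4 blind plausibly covers bench decisions such as re-runs, the GC-sensor algorithm is called well defined, and 10.7 includes every participant whose VOC analysis is completed. These reduce the concern but do not remove it. The blind does not reach the analysts, the modelling tools are left open, and 10.7 does not say what makes an analysis complete or who judges it.

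**Data lock and label release belong in the SAP.** Silence on these alone would be no finding. But the protocol itself fixes where the comparison is done and has GCMS reports built by diagnosis before alignment. Those are statements to be reconciled with 7.4, not omitted detail.

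**The size is hypothetical.** Agreed. The number of variants, their correlation and the one-sided 2.5% test are all assumptions; 10.1 says only a 0.05 significance level.

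**Conclusion.** The concern holds in a limited form. The stool analysis and the primary VOC comparison are both placed with a university that has a disclosed commercial interest in the GC-sensor. The blind stops at laboratory staff, and GCMS processing as written uses the diagnosis before alignment. It is unclear whether the LSTM statistician has any part in the comparison.

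This shows that processing with diagnoses known is not prevented. It does not show that it is intended, or that any result would be biased. The size of any bias cannot be derived from the documents; the 1.4 to 4.2 points above depend on the assumed number of variants, their correlation, and selection after accuracy has been seen. The point is a worthwhile, inexpensive protection, not a flaw that invalidates the design.

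**What to change.** Reconcile sections 5, 7.4, 7.11 and 11.2 so that:

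1. Diagnoses stay at LSTM until the University of Liverpool has completed and locked the processed VOC data from both methods, including all run exclusions, together with the primary analysis script.
2. GCMS reports are generated and aligned without reference to diagnostic group.
3. The study statistician then links the diagnoses and runs the locked script for the primary IBD versus non-IBD comparison.
4. Any later change to the pipeline is labelled exploratory.

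In 13.8, state how the nil declaration applies to any TMG member employed by the owning university.

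The cost is protocol wording, a hand-over of the script and a few days of a statistician already on the team. Clinical data are already managed at LSTM, so part of the arrangement is in place. The real downside is that the laboratory cannot retune the pipeline for the primary result once diagnoses are released.
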